10. MEASUREMENT OF EFFECT

Response and progression of CLL participants will be evaluated using the 2018 iwCLL criteria for CLL.¹

The same method of assessment and the same technique should be used to characterize each identified and reported lesion at baseline and during follow-up. Imaging-based evaluation is preferred to evaluation by clinical examination when both methods have been used to assess the anti-tumor effect of a treatment.

Clinical lesions will only be considered measurable when they are superficial (e.g., skin nodules and palpable lymph nodes). For the case of skin lesions, documentation by color photography, including a ruler to estimate the size of the lesion, is recommended. All lymph node measurements should be taken and recorded in metric notation, using a ruler, calipers, or digital measurement tool.

10.1 Imaging Evaluations

All participants will have screening CT or MRI scans of the chest, abdomen, and pelvis within 30 days prior to the start of protocol therapy. Scans will be repeated on day 28 (\pm 7 day scheduling window) of cycles 2, 6, 12, 17, and 24, as well as at the off-treatment visit. Cycle 17 scan may be omitted for participants in confirmed CR at the treating investigator's discretion.

In addition, scans will be repeated at any point to confirm a CR and in any participant with suspected relapse following achievement of CR (if not done within the prior three months). Participants who undergo re-treatment will have scans on day 28 of re-treatment cycles 2, 6, and 12 as well as at the off-treatment visit (\pm 7 day scheduling window). Scans may also be repeated at any other time at the discretion of the treating investigator.

Conventional CT and MRI should be performed. These techniques should be performed with cuts of 10 mm or less in slice thickness contiguously. Spiral CT should be performed using a 5 mm contiguous reconstruction algorithm.

10.2 Bone Marrow Biopsy / Aspirate

Screening bone marrow biopsy / aspirate is required for all participants and may be obtained up to 90 days prior to the start of protocol therapy as long as no intervening therapy has occurred. Repeat bone marrow biopsy / aspirate is required on day 1 of cycles 7, 13, and 25 (i.e. at the completion of 24 cycles of therapy), with an allowable \pm 7 day window (cycle 7 day 1 bone marrow must be performed prior to the initiation of ublituximab therapy). Bone marrow biopsy / aspirate is also required at any point to confirm a CR, at the time of suspected relapse following achievement of CR (if not done within the prior 6 months), and on re-treatment cycle 13 day 1 for participants who undergo re-treatment (\pm 7 day window). Bone marrow biopsy / aspirate may also be done at any time at the treating investigator's discretion.

10.3 Response Criteria

Table 24: Response Definition Following Treatment of CLL Participants					
Group	Parameter	Complete Remission (CR) ¹	Partial Remission (PR) ²	Stable Disease (SD) ³	Progressive Disease (PD) ⁴
A	Lymph nodes	None \geq 1.5 cm	Decrease \geq 50% (from baseline) ⁵	Change of -49% to +49%	Increase \geq 50% from baseline or from response
	Liver and/or spleen size ⁶	Spleen size $<$ 13 cm; liver size normal	Decrease \geq 50% (from baseline)	Change of -49% to +49%	Increase \geq 50% from baseline or from response
	Constitutional symptoms	None	Any	Any	Any
	Circulating lymphocyte count	Normal	Decrease \geq 50% from baseline	Change of -49% to +49%	Increase \geq 50% from Baseline
B	Platelet count	$\geq 100 \times 10^9/L$ or increase \geq 50% over baseline		Change of -49% to +49%	Decrease of \geq 50% from baseline secondary to CLL
	Hemoglobin	$\geq 11.0 \text{ g/dL}$ (untransfused and without erythropoietin)	$\geq 11 \text{ g/dL}$ or increase \geq 50% over baseline	Increase $< 11.0 \text{ g/dL}$ or $< 50\%$ over baseline, or decrease $< 2 \text{ g/dL}$	Decrease of $\geq 2 \text{ g/dL}$ from baseline secondary to CLL
	Marrow	Normocellular, no CLL cells, no B-lymphoid nodules	Presence of CLL cells, or of B-lymphoid nodules, or not done	No change in marrow infiltrate	Increase of CLL cells by $\geq 50\%$ on successive biopsies

 1. For CR, all criteria have to be met from groups A and B. 2. For PR, at least 2 of the parameters of group A and 1 parameter of group B need to improve if previously abnormal; if only 1 parameter of both groups A and B is abnormal before therapy, only 1 needs to improve. 3. For SD, all of the criteria have to be met. 4. For PD, at least 1 of the criteria of group A or group B has to be met. 5. Sum of the products of 6 or fewer lymph nodes (as evaluated by CT scans and physical examination in clinical trials or by physical examination in general practice). 6. Spleen size is considered normal if $< 13 \text{ cm}$. There is no firmly established international consensus on the size of a normal liver; therefore, liver size should be evaluated by imaging and manual palpation in accordance with local standard of care guidelines. 					

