Targeting the B-cell receptor pathway with either inhibitors of BTK or PI3K δ is highly effective for the treatment of CLL. However, deep remissions are uncommon, and drug resistance with single-agent therapy can occur. *In vitro* studies support the effectiveness of combining PI3K δ and BTK inhibitors in CLL.¹⁰ Combination treatment for dual blockade of pathways downstream of BCR could increase the effectiveness of each single agent, enable lower dose administration thus minimizing side effects, and potentially prevent drug-resistance. The combination of ibrutinib and idelalisib has been shown to synergistically inhibit *in-vitro* BCR-controlled adhesion in both mantle cell lymphoma (MCL) cell lines and primary MCL and CLL cells. This is a crucial mechanism of cell survival and likely explains the surge in lymphocytosis after BTK/PI3K-inhibitor administration.¹⁰ This combination may increase initial lymphocytosis even further,

although this would not be clinically meaningful. The combination of acalabrutinib, a highly specific BTK inhibitor, with a different PI3K inhibitor (ACP-319) in a CLL mouse model resulted in significantly larger reductions in tumor burden and survival compared to single-agent therapy. It also reduced phosphorylation of pathways downstream of NF- κ B signaling.¹¹ Our group has recently combined ibrutinib with umbralisib and found that the combination was tolerable, with encouraging PFS and an early suggestion of higher CR rate.¹²

Ublituximab is a type I, chimeric, glycoengineered anti-CD20 monoclonal antibody that causes increased ADCC activity against B cells and shows activity as a single-agent in relapsed NHL and CLL patients, with an overall response rate of 50%.¹³ A phase 2 study of its combination with ibrutinib in 45 patients with relapsed CLL showed a 90% PR rate at 6 months, due to clearance of lymphocytosis that is usually seen with ibrutinib alone. The combination was well tolerated. The most common AEs were infusion-related reactions (IRRs), diarrhea, fatigue, nausea, and rash. Grade 3/4 AEs were mainly hematological (7-11% cytopenias) and IRRs, and 9% of subjects discontinued study due to AEs.¹⁴

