4. TREATMENT PLAN

4.1 Treatment Regimen

A treatment cycle is defined as 28 consecutive days. Treatment will be administered on an outpatient basis. Reported adverse events and potential risks are described in **Section 7**. Appropriate dose modifications are described in **Section 6**.

Participants will receive acalabrutinib at the FDA approved dose of 100 mg by mouth twice daily and umbralisib at 800 mg by mouth once daily continuously throughout each treatment cycle. Ublituximab will be given IV starting with cycle 7 on days 1, 2, 8, and 15 and cycles 8-12 on day 1.

Participants who are in bone marrow and CT confirmed CR at the end of cycle 12 will stop dosing with acalabrutinib and umbralisib.. Participants not in CR will continue to cycles 13-24.

Participants will have peripheral blood monitoring for MRD as described in the **Study Calendar** in **Section 10**. If early relapse or recurrence is detected, the patient will undergo restaging with a CT scan and a bone marrow biopsy / aspirate. At the discretion of the treating investigator, patients with early relapse not meeting iwCLL criteria for retreatment may resume dosing with acalabrutinib and umbralisib until further disease progression, unacceptable toxicity, or other criteria are met as described in **Section 5.5**. The study agents will be resumed at the dose levels the participant was receiving prior to discontinuation. Dosing will resume for a maximum of 12 additional treatment cycles, such that participants may receive a maximum total of 36 cycles of study therapy.

Table 4: Regimen Description

Agent	Premedications; Precautions	Dose	Route	Schedule ¹	Cycle Length
Acalabrutinib	May be taken with or without food.	100 mg	By mouth	Twice Daily	
Umbralisib	Take within 30 minutes of a meal. Participants are required to receive prophylactic anti-viral and anti-pneumocystis jiroveci pneumonia (PJP) treatment, refer to Section 5.4 .	800 mg	By mouth	Once Daily	28 days

Table 4: Regimen Description

Agent	Premedications; Precautions	Dose	Route	Schedule ¹	Cycle Length

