10.4 Definitions

Treatment Failure: Responses that should be considered clinically beneficial include CR and PR; all others (e.g., stable disease, non-response, PD, death from any cause) should be rated as a treatment failure.

Overall Survival (OS): Defined as the time from first treatment day to death due to any cause, or censored at date last known alive.

Progression-Free Survival (PFS): Defined as the time from first treatment day to the earlier of progression or death due to any cause. Participants alive without disease progression are censored at date of last disease evaluation.

Event-Free Survival (EFS): Defined as the interval between the first treatment day to the first sign of disease progression or start of a new treatment or withdrawal from the trial because of toxicity or death (whichever occurs first).

Time to Next Treatment (TTNT): Defined as the interval between the first treatment day until the patient starts an alternative therapy for progressive CLL.

Relapse: Defined as evidence of disease progression in a patient who has previously achieved the above criteria of a CR or PR for ≥ 6 months.

Refractory Disease: Defined as treatment failure or as progression within 6 months from the last dose of therapy.

Minimal Residual Disease (MRD)-Negative: Blood or marrow with < 1 CLL cell per 10,000 leukocytes assessed by at least four color flow cytometry (MRD flow), allele-specific oligonucleotide PCR, or high-throughput sequencing using the ClonoSEQ assay.

Complete Remission with incomplete marrow recovery (CRi): Some patients fulfill all the criteria for a CR, but have a persistent anemia, thrombocytopenia or neutropenia apparently unrelated to CLL, but related to drug toxicity. These patients should be considered as a different category of remission, CR with incomplete marrow recovery (CRi). The marrow evaluation should be performed with scrutiny and not show any clonal disease infiltrate.

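### Table 24 counts a lone lymphocyte rise of at least 50% as progression, with no exemption for the drug-related lymphocytosis that Section 2.1 anticipates

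*Combined protocol and SAP*

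**What the plan says.** In Table 24 (Section 10.3) the circulating lymphocyte count is one of the group A parameters. Its PD entry is an increase of at least 50% over baseline, with no condition on cause or timing. Footnote 4 reads "For PD, at least 1 of the criteria of group A or group B has to be met". The platelet and hemoglobin PD entries do carry a condition on cause: the fall must be "from baseline secondary to CLL". Footnote 2 sets the PR rule: "For PR, at least 2 of the parameters of group A and 1 parameter of group B need to improve if previously abnormal". A fall in lymphocytes is not required for PR.

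Section 2.1, discussing ibrutinib with idelalisib (the same two drug classes), describes an effect on cell adhesion that "likely explains the surge in lymphocytosis after BTK/PI3K-inhibitor administration". It continues "This combination may increase initial lymphocytosis even further", and adds "although this would not be clinically meaningful".

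Section 4.1 starts acalabrutinib and umbralisib at cycle 1, but "Ublituximab will be given IV starting with cycle 7". Re-treatment after relapse, also in Section 4.1, again gives the two inhibitors without the antibody.

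Section 10.4 makes progression a PFS and an EFS event. On treatment failure it says "Responses that should be considered clinically beneficial include CR and PR; all others", and rates the rest, PD included, as failure. Section 4.5 makes progression a reason to stop protocol therapy, with an exception only for relapse after confirmed CR and treatment discontinuation. Section 10 names the 2018 iwCLL criteria as the basis for response and progression.

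**The concern.** The table treats as progression a change that the protocol's own rationale attributes to the drug classes under study and regards as harmless. The design also leaves a long stretch in which it could show. Section 2.1 credits ublituximab with clearing the lymphocytosis usually seen on ibrutinib alone, yet here the antibody is held back for six cycles, and scans at the end of cycles 2 and 6 fall before it starts.

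The protocol's background counts PR with lymphocytosis as a response, for single-agent umbralisib in Section 2.2.3.1 and in the response definition for the umbralisib-ibrutinib doublet in Section 2.5. This protocol has no such category.

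If the table is followed as printed, a responding participant can be given an early PFS and EFS event, be rated a treatment failure, and be taken off therapy. If some sites follow the table and others apply an exemption that these documents do not contain, the same blood count is scored differently by site. Central review under Section 10.5 covers scan results only, so it would not reconcile lymphocyte calls.

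**Working it through.** The plan states no figure on this point. The check is a reading of the table, followed by the effect of one misclassified participant.

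**1. Does the table give two answers?** Take assumed values, with the improving parameters abnormal at baseline:

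| Parameter | Change | Table 24 reading |
|---|---|---|
| Nodes (group A) | -60% | meets PR entry (fall of at least 50%) |
| Spleen (group A) | -60% | meets PR entry (fall of at least 50%) |
| Hemoglobin (group B) | 10 to 11.5 g/dL | meets PR entry (at least 11 g/dL) |
| Lymphocytes (group A) | 50 to 80 ×10⁹/L | meets PD entry |

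The lymphocyte change is 80/50 − 1 = +60%; for a baseline of 50 the PD threshold is 50 × 1.5 = 75 ×10⁹/L. Two group A parameters and one group B parameter have improved, so footnote 2 gives PR. One group A criterion for PD is met, so footnote 4 gives PD. No footnote, no definition in Section 10.4 and nothing in Section 12 says which prevails.

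**2. Length of the window.** Six cycles of 28 days: 6 × 28 = 168 days of both inhibitors without antibody. This is the period in which the situation can arise. Section 2.1 does not say how long the lymphocytosis lasts, so it is not shown that the whole period is at risk. Re-treatment opens a similar window, although Table 24 does not say which count serves as baseline there.

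**3. How often?** The documents give no rate of a 50% rise. Two related figures exist:

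- Section 2.2.3.1: 7 of 20 participants with CLL (35%; exact 95% interval 15% to 59%) had PR with lymphocytosis on umbralisib alone. That is a response category and not a count of participants whose lymphocytes rose by half.
- Section 2.5: on umbralisib with ibrutinib, 6 CR + 13 PR = 19, which is every CLL responder. None was left as PR with lymphocytosis, so the problem may be confined to early assessments.

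**4. Effect per false event on two-year PFS.** Inputs: 30 per cohort (Section 12.2); an assumed true two-year PFS of 90%, borrowed from the doublet in Section 2.5; and an assumption of no censoring before month 24. The Kaplan-Meier estimate is then the number progression-free at month 24 divided by 30.

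| False events during cycles 1–6 | Two-year PFS |
|---|---|
| 0 | 27/30 = 90.0% |
| 1 | 26/30 = 86.7% |
| 2 | 25/30 = 83.3% |
| 3 | 24/30 = 80.0% |

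Each costs 1/30 = 3.3 points, provided the participant would otherwise have been progression-free at two years. If the participant would have progressed before month 24 anyway, the estimate stays at 27/30 and the event only moves earlier.

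**The case against.** The strongest reply is that Table 24 sits under Section 10, which says that the 2018 iwCLL criteria govern response and progression, and that Section 2.1 already tells investigators the rise is not meaningful. A trained assessor may well not call PD on lymphocytes alone. This stands as a reason to doubt that the table would be applied literally everywhere. It does not remove the problem: these documents print their own table, write no exemption into it, and do not say whether the table or the cited criteria prevail.

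It is also fair that nothing inferential is touched. The primary endpoint is CR after 24 cycles. Section 12.5 describes the secondary analyses, PFS included, as primarily descriptive, and there is no comparator. The 3.3 points is simply one participant in 30 and says nothing about likelihood. Section 5.5 records that supply of umbralisib and ublituximab ended in March 2023, so wrongful removal from therapy is largely a past risk. All of this stands and limits the weight of the point.

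A reader might go further in two directions that the documents do not support. One is that about a third of participants would be miscalled: the 7 of 20 figure is not a rate of PD under Table 24. The other is that the CR test loses power: that would need a share of eventual CRs lost to an early PD call, and no such share is given or can be derived.

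**Conclusion.** The point holds as a defect in a written rule. By its own footnotes Table 24 makes an isolated lymphocyte rise of at least 50% sufficient for PD, and it can return PR and PD for the same participant without precedence. That conclusion rests on the text alone and not on any assumed rate.

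The consequence is conditional on literal or inconsistent application. It is confined to scoring PFS, EFS, response and treatment failure, chiefly in data from cycles 1 to 6 and from any re-treatment. The loss of 3.3 points of two-year PFS per false event assumes 30 per cohort, no censoring before two years, 90% true PFS and a participant otherwise progression-free; the number of such events is unknown and may be zero. No effect on the CR decision rule is shown. It merits correction because the remedy is small. Confidence is moderate, since the documents cannot show how assessors actually applied the table.

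**What to change.** Add a footnote to Table 24 to this effect: lymphocytosis arising after starting or restarting acalabrutinib or umbralisib, without any other group A or group B progression criterion, is not PD for response, PFS, EFS or Section 4.5; this footnote prevails over footnote 4; the exemption ends once the count has met the PR or CR lymphocyte entry, and applies anew at re-treatment.

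Alongside it:

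- Record a participant who otherwise meets PR as PR with lymphocytosis. Report this category separately from the PR rate in Sections 1.3 and 12.5, and state in Section 10.4 that it is not treatment failure.
- Apply the rule to every participant's recorded counts and response calls. Reviewing only PD calls in an open-label trial could move PFS in one direction only.
- Report PFS under both the printed rule and the revised rule.
- Where a participant left therapy on a lymphocyte-only PD call, censor at the last adequate disease evaluation if later progression cannot be dated. Such participants have an off-treatment scan and then follow-up by record review, telephone or care-provider contact.

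The cost is one footnote, a few words in Section 10.4, one CRF response category and a second PFS analysis. Table 20 already captures blood counts with differential at all visits in cycles 1 to 12, so the counts for those cycles are in hand, although dates of later progression may not be.

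The downside is that a true blood-only progression during the initial surge may be recognised later, or never by lymphocyte count alone if the count does not reach the PR entry. The scans at the end of cycles 2 and 6, the cycle 7 marrow, and the hemoglobin and platelet criteria limit this only in part.

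### Table 24's spleen and node cells conflict: a normalised spleen can miss the PR cell, and CR-level nodes or spleen can count as PD, with no precedence rule

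*Combined protocol and SAP*

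**What the plan says.** Section 10 makes the 2018 iwCLL criteria governing, and Table 24 in section 10.3 is the version written into the protocol. The cells at issue are:

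- **Liver/spleen, CR:** absolute, spleen below "13 cm; liver size normal". Footnote 6 reads "Spleen size is considered normal if" below that same limit.
- **Nodes, CR:** absolute, no node of 1.5 cm or larger.
- **Both rows, PR:** a decrease of at least "50% (from baseline").
- **Both rows, SD:** "Change of -49% to +49" percent.
- **Both rows, PD:** an increase of at least "50% from baseline or from response", with no minimum size.

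Footnote 5, attached to the nodal PR cell, gives the node metric as "Sum of the products of 6 or fewer lymph nodes".

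The footnotes combine the rows. Footnote 1: "For CR, all criteria have to be met from groups A and B". Footnote 2, for PR: "at least 2 of the parameters of group A and 1 parameter of group B need to improve if previously abnormal". Footnote 3 requires every SD criterion for SD. Footnote 4 makes a single criterion from either group enough for PD.

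Section 10.4 counts only CR and PR as clinically beneficial and rates everything else as treatment failure. It also builds PFS, EFS and relapse on progression. Section 4.5 lists progression among the reasons to come off protocol therapy. Nowhere do the documents say which category applies when the conditions for two are met.

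**The concern.** The CR cells of these two rows are fixed sizes, while the PR, SD and PD cells are percentages of whatever was there before. Nothing joins the two scales. One would expect a parameter good enough for CR to be good enough for PR, and a parameter at CR level not to be PD at the same scan. Table 24 guarantees neither.

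The PR rate after 24 cycles is part of the first secondary objective (section 1.3). Section 12.5 adds best achieved PR and tests clinical response against prognostic factors. A responder who cannot be placed in any category is lost from these analyses, or is placed by whoever reads the case. PD feeds PFS and relapse, so an unintended PD at CR-level size would bring those events forward. Because the PD reference may be the response value, participants left with small residual nodes are the most exposed.

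**Working it through.** The plan states no figure that depends on this, so there is none to reproduce. The inputs are the 13 cm, 1.5 cm and 50% limits of Table 24.

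**Spleen, PR against CR.** For baseline size S, the PR cell needs a final size of at most 0.5 x S and the CR cell needs less than 13 cm. PR is the stricter cell when 0.5 x S < 13, that is, S < 26 cm. Footnote 2 asks for improvement only where the parameter was abnormal, so the range that matters is 13 to under 26 cm.

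| Baseline (cm) | Decrease needed for CR cell, 1 - 13/S | Change if it reaches 12.9 cm | Size needed for PR cell (cm) |
|---|---|---|---|
| 14 | more than 7.1% | -7.9% | 7 |
| 16 | more than 18.8% | -19.4% | 8 |
| 18 | more than 27.8% | -28.3% | 9 |
| 20 | more than 35.0% | -35.5% | 10 |
| 24 | more than 45.8% | -46.3% | 12 |

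Every row meets the CR cell at 12.9 cm, falls in the SD band and fails the PR cell. At 26 cm the two limits meet at 13 cm. Above that PR is the easier cell: at 30 cm, PR needs 15 cm, while CR needs a decrease of more than 56.7%.

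**A participant with no category.** Suppose that only spleen and lymphocytes are abnormal in group A. The spleen goes from 20 to 12.5 cm, (12.5 - 20)/20 = -37.5%. Lymphocytes fall by at least 50% to normal. The marrow still shows CLL, and nothing has worsened.

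- CR: no, because the marrow criterion fails.
- PR: no. Two group A parameters must improve, and the spleen falls short of 50%.
- SD: no. The lymphocyte fall lies outside the SD band, and SD needs every criterion.
- PD: no.

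Under section 10.4 this participant is a treatment failure.

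**Nodes, PD against CR.** Take nodes of equal diameters. The product rises by 50% when each diameter rises by a factor of sqrt(1.5) = 1.225. If all followed nodes go from 1.0 to 1.23 cm, the sum rises by 1.23^2 - 1 = 51%, which is PD, with no node at 1.5 cm. With uniform growth this is possible from any starting diameter below 1.5/1.225 = 1.22 cm. If PD were read on a single diameter instead, the start would have to be below 1.5/1.5 = 1.0 cm.

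The sum of products limits this. With six nodes of 1.0 cm the sum is 6 and PD needs 9, a rise of 3. One node growing alone would need a product of 1 + 3 = 4, that is 2.0 cm, which already breaks the CR cell. A node kept below 1.5 cm adds less than 2.25 - 1 = 1.25, so two nodes add less than 2.5 and cannot do it. Three can: each needs a product of 2, or 1.41 cm.

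**Spleen, PD against CR.** From 8 to 12 cm is 12/8 - 1 = +50%, hence PD, with the spleen still below 13 cm. The overlap exists for any reference size below 13/1.5 = 8.7 cm.

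**The case against.** The strongest reply is that the 2018 iwCLL criteria govern and may supply a minimum size, a baseline rule for the spleen, or an order of precedence. Their full text is not in the documents, so this cannot be settled here. It does not remove the point: if the source has such rules, Table 24 omits them, and if it does not, the protocol needs its own. One may also say that footnote 2 only asks parameters to improve, so a normalised spleen counts. That is a sensible reading, but the PR cell does not say it.

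Several stronger readings are tempting, and the documents do not support them:

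- **That PR as a category is harder to reach than CR.** The inversion is confined to one row. CR needs every criterion, including a clear marrow, whereas PR can be reached through nodes and lymphocytes without the spleen. Likewise, a spleen in the SD band does not make the participant SD.
- **That every spleen under 26 cm is affected.** Below 13 cm the spleen is normal, and footnote 2 does not ask for improvement.
- **That one node growing from 1.0 to 1.23 cm is PD.** Under footnote 5's metric this holds only if it is the sole node followed.
- **That persistent lymphocytosis leaves spleen and nodes to decide PR at cycle 24.** Section 2.1 reports that adding ublituximab to ibrutinib cleared lymphocytosis, and section 4.1 gives ublituximab in cycles 7 to 12. The worked case above does not rely on lymphocytosis.
- **That the primary result is distorted.** The spleen PR cell cannot alter the CR count or the rules of 10 and 13 CRs in section 12.4.

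Secondary analyses are also mainly descriptive (section 12.5), and scan results are reviewed centrally (section 10.5). Both limit the damage, but a central reader needs a consistent rule too.

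**Conclusion.** The inconsistency stands, at the level of individual cells. For an abnormal baseline spleen of 13 to under 26 cm, the PR cell is stricter than the CR cell. Where the spleen is one of the group A parameters needed for PR, a responder with residual marrow disease can fall outside all four categories and be rated a treatment failure. Separately, nodes and small spleens can meet PD while meeting their CR cell, and nothing says which prevails.

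The effect is on the secondary PR rate, PFS, EFS and relapse. It reaches the primary CR count only if an overlapping PD is allowed to override CR. The documents give no distribution of spleen or node sizes, so the number affected cannot be estimated.

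The conclusion assumes that the percentages apply to total size, as the table is worded. The node figures further assume equal diameters and, except where a single diameter is named, that footnote 5's metric also governs PD.

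**What to change.** 1. For endpoint derivation, add to Table 24 that a parameter meeting its CR cell (spleen below 13 cm; all nodes below 1.5 cm) also meets the PR cell for that parameter. Both limits are the protocol's own. This places the worked case in PR, provided its group B condition is met.
2. Reconcile the CR and PD cells for nodes and spleen with each other and with the 2018 iwCLL criteria, and say whether footnote 5's metric applies to PD.
3. State which category prevails when the conditions for CR and PD are both met.

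No new PD threshold is proposed. Measuring spleen change only above 13 cm, or adding a minimum absolute increase, has no basis in the documents, and PD is also an off-therapy criterion in section 4.5. The passages need reconciling by the sponsor.

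The cost is wording in one table and a small change to the derivation code. No new measurements are needed.
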